4.0 TREATMENT PLAN

This is a single arm, open label, phase II study of ibrutinib, nivolumab and blinatumomab in patients with RT.

[figure not shown]

Figure 4. Schematic of treatment plan

Patients will receive treatment as follows:

1. 2 cycles of 3 drug combination (ibrutinib, nivolumab and blinatumomab). These cycles will be 8 weeks each.
2. 9 cycles of 2 drug combination (ibrutinib and nivolumab). These cycles will be 4 weeks each.
3. Maintenance treatment with ibrutinib monotherapy until disease progression following completion of nivolumab.

4.1 Ibrutinib therapy.

Ibrutinib treatment will commence on cycle 1, day 1 at 420mg/d. Dose reductions to 280mg/d or 140mg/d are allowed per treating physician discretion, but the reason must be documented in the medical record. Ibrutinib will be given continuously until disease progression or toxicity.

4.2 Nivolumab therapy.

Patients will receive nivolumab for up to a total of 52 weeks. Dosing will be 240mg IV every 2 weeks, commencing on day 1 until 2nd response assessment, then 480mg IV every 4 weeks.

4.3 Blinatumomab therapy

Patients will receive blinatumomab as a continuous IV infusion, commencing on day 15 of cycle 1 and day 1 of cycle 2, for 2 courses of 4 weeks each separated by a 2 week blinatumomab treatment-free interval.

In cycle 1 and cycle 2 of blinatumomab, dexamethasone pre-medication will be given as outlined in table 1, below.

Table 1. Dexamethasone treatment during the study

Treatment phase	Target patient	Dexamethasone dose
Screening	Patients with bulky or rapidly-progressive disease	Dose and duration at the discretion of the investigator
Pre-dose dexamethasone before cycle 1 and 2 of blinatumomab and before dose-escalation	All patients (before each blinatumomab cycle and dose increase)	Dexamethasone 20 mg IV/PO 12-24 hours prior to and within 1 hour before start of blinatumomab treatment in each treatment cycle, and before dose increase
During cycle 1 and 2 for the first 48 hours of blinatumomab and after each dose escalation	All patients, for the first 48 hours of each treatment cycle	Dexamethasone 8mg IV/PO Q8 hours for 48 hours.
Infusion interruption/dose modification due to adverse event	Patients who interrupt treatment > 4 hours	Dexamethasone 20 mg IV/PO 12-24 hours prior to and within 1 hour before re-start of blinatumomab treatment
In case of signs of cytokine release (CRS) of grade ≥2 (see Appendix C for grading of CRS and Appendix D for definition of high dose vasopressors)*	Patients with signs of CRS	Principal Investigator must be notified. Dexamethasone IV/PO at a dose of at least 24mg per day. The dose should then be reduced step-wise over approximately 4 days, provided signs of CRS have

		improved/resolved.
In case of CNS event grade ≥ 2 (See Appendix E for grading)*	Patients with CNS-related AE	Principal Investigator must be notified. Dexamethasone should be administered at a dose of at least 24mg/day. Dexamethasone should be reduced step-wise over approximately 4 days, provided neurological toxicity has improved/resolved.

*Please note that when dexamethasone is given for the management of toxicity, the above dexamethasone doses are a guideline. Management of dexamethasone dosing should be individualized according to the severity of toxicity and the patient's response. This management should be at the investigator's discretion.

In cycle 1 of blinatumomab, patients will be hospitalized on day 15-31 (for the first 17 days of blinatumomab therapy). To mitigate for potential CRS and CNS events associated with introduction of blinatumomab, in cycle 1, blinatumomab will be initiated at 9mcg/day from day 15-21, followed by 28 mcg/day from day 22-28. This will be followed by 112 mcg/day from day 29-42. In cycle 2, patients will be admitted for the first 3 days. Blinatumomab in cycle 2 will be administered at a dose of 112 mcg/day from day 1-28.

4.4 Response assessment

Formal response assessment will take place 2weeks (+/- 1 week) following completion of the first course of blinatumomab.. Response assessment will comprise laboratory evaluation (CBC), bone marrow examination and PETCT scan. Responses in RT for the primary study endpoint will be assessed according to the Lugano criteria¹⁹ and, as an exploratory endpoint, in co-existing CLL, according to 2018 IWCLL response criteria. Responses in RT will be assessed separately from responses in CLL. Any nodal or extranodal lesion with SUV ≥ 5.0 on PETCT will be considered indicative of RT, for the purposes of response assessment. Lesions with SUV <5.0 pre-treatment will be considered to be due to CLL, rather than RT; residual PET avidity in such lesions post-treatment will not be considered evidence of failure of control of RT, provided SUV remains <5.0 . In order for CR to be attained, all lesions with SUV ≥ 5.0 pre-treatment must be PET negative post-treatment and there must be no new PET avid lesions, unless these are proven by biopsy not to be due to Richter

Transformation. PET characterization of target lesions as due to CLL or RT pre-treatment will allow separate response assessment for RT (the primary end point) and CLL (an exploratory endpoint), without discrepancies arising due to the differences in response criteria. When possible, biopsy of residual RT sites will be requested to evaluate for residual disease.

Please note that there may be instances where PETCT is not able to be performed. In these instances, CT scan will be performed instead (see section 8.0 and 9.0)

A second response assessment will be undertaken 4 weeks (+/-1 week) after completion of the consolidation cycle.

4.5 Allogeneic stem cell transplantation.

In patients where a suitable donor is identified and who are considered eligible, allogeneic stem cell transplantation may be offered any time after completion of the first cycle of blinatumomab and initial response assessment. Patients will be considered “off study” on the date they commence pre-transplant conditioning chemotherapy. If the patient agrees, they will be enrolled on a departmental umbrella protocol (DR09-0223) to continue to follow them for overall survival.

4.6 Surveillance after completion of blinatumomab.

After completing blinatumomab, patients will have PETCT every 3 months until completion of nivolumab therapy. If PETCT cannot be performed, for whatever reason, CT with oral and IV contrast (unless contraindicated) will be performed instead.

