1.0 OBJECTIVES AND STUDY ENDPOINTS

Primary endpoint

1. Determine the overall response rate (complete remission plus partial remission) in Richter transformation (RT) after 2 courses of blinatumomab, ibrutinib and nivolumab treatment.

Secondary endpoints

1. Assess the safety and feasibility of administering blinatumomab combined with ibrutinib and nivolumab to patients with RT.
2. Determine the complete remission rate for RT after 1 and 2 courses of therapy.
3. Determine the progression-free survival rate for RT at 1 year.
4. Determine the overall survival rate for RT at 1 year.
5. Determine the proportion of patients who proceed to allogeneic stem cell transplantation as next treatment.

Exploratory objectives

1. Pre- and post-treatment (progression) tumor biopsies for immunologic analysis, including immune checkpoint expression by tumor and by infiltrating T cells, flow cytometry and RNA-sequencing analysis (including the potential to perform single cell RNA-seq) or array-based analysis of immune cell subsets.
1. Immune checkpoint expression by circulating T cells and T cell subset analysis.
2. “Liquid biopsy” using circulating tumor DNA analysis and comparison with mutational profile identified in concurrent CLL specimen and tumor biopsy. This will also be used as an MRD analysis tool.

Correlation of RT microRNA profile with response to treatment and outcomes.

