2.0 BACKGROUND AND RATIONALE

2.1 Richter Transformation

RT is defined as the transformation of CLL into a more aggressive lymphoma; while this is most commonly diffuse large B cell lymphoma (DLBCL) histology, rare cases of transformation to Hodgkin Lymphoma (HL)¹ histology are recognized. A large series, comprising all newly diagnosed CLL patients seen at the Mayo Clinic over 12 years, demonstrated that 2.3% of patients subsequently

developed biopsy-proven RT, at a rate of 0.5% per year; almost half had never required treatment for CLL prior to the diagnosis of RT.² Clinicopathologic features suggestive of the diagnosis include high fever, weight loss, rapidly enlarging lymph nodes, hypercalcemia and elevated LDH.³ There is an ongoing incidence of RT seen in patients treated with highly effective, novel, targeted therapies for CLL, such as ibrutinib⁴ and venetoclax.⁵

Prognosis is determined by both genetic and clinical features. Approximately 80% of DLBCL transformations are clonally related to the underlying CLL; the 20% with clonally unrelated DLBCL have a significantly better prognosis. Clonal relationship can be determined by comparing the sequences of the *IGHV* gene of the lymphoma to that of untransformed CLL cells. Two clinical prognostic models have been developed,^{6, 7} the latter of which also demonstrated the importance of *TP53* disruption as a negative prognostic feature.

Treatment is generally unsatisfactory. Moderate to high-intensity chemoimmunotherapy regimens have produced CR rates of 5-38%, with median survival in most series of <1 year.⁸⁻¹² *TP53* disruption likely plays a major role in chemotherapy resistance. A minority of patients achieved long-term survival after allogeneic stem cell transplantation (alloSCT),⁶ but most patients are not eligible for this treatment due to age, co-morbidities, lack of appropriate donor, and/or failure to achieve a response to initial treatment. Nonetheless, long-term survival after alloSCT in a subgroup of patients suggests that immunologic control is possible. More effective therapy is urgently needed in order to increase the proportion of patients able to undergo alloSCT and to achieve more durable disease control in those patients who are not candidates for alloSCT.

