10.0 CRITERIA FOR RESPONSE

10.1 Richter's Transformation

Response assessment in RT will be performed according to the Lugano criteria for diffuse large B-cell lymphoma, as outlined in Appendix H.

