10.2 Response Criteria in Chronic Lymphocytic Leukemia

The response of the co-existing CLL will be assessed according to the 2018 IWCLL criteria, which are re-produced in appendix I Overall response is defined as a CR or PR. Patients with missing or no response assessment will be classified as non-responders. The full criteria are re-produced below. The co-existence of RT may result in difficulty determining whether residual nodal, splenic or hepatic enlargement is due to persistent RT or CLL. For the purposes of response assessment, PET criteria

will be used to distinguish the two. However, if diagnostic difficulty exists, biopsy may be required.

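### Does a patient who goes to transplant before finishing course 2 lack a defined result in the primary response rate?

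*Combined protocol and SAP*

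**What the plan says.** Section 1.0 sets the primary endpoint: "Determine the overall response rate (complete remission plus partial remission) in Richter transformation (RT) after 2 courses of blinatumomab, ibrutinib and nivolumab treatment". Section 14.0 repeats that response is judged once both blinatumomab courses are finished. The secondary endpoints include "Determine the complete remission rate for RT after 1 and 2 courses of therapy" and "Determine the proportion of patients who proceed to allogeneic stem cell transplantation as next treatment".

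Section 10.1 is a single sentence: "Response assessment in RT will be performed according to the Lugano criteria for diffuse large B-cell lymphoma, as outlined in Appendix H". The Lugano table in Appendix H has no category for an assessment that was not done. Section 10.2, on CLL, defines overall response as CR or PR and then states: "Patients with missing or no response assessment will be classified as non-responders". Section 4.4 says "Responses in RT will be assessed separately from responses in CLL" and calls the CLL response exploratory.

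Section 4.5 states that, for eligible patients with a suitable donor, "allogeneic stem cell transplantation may be offered any time after completion of the first cycle of blinatumomab and initial response assessment". The patient is off study from the start of conditioning and, if he or she agrees, is then followed for overall survival under another protocol. Section 12.0 also lists transplant as a reason for removal.

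**The concern.** The protocol foresees the event. Section 2.1 gives as motivation that "More effective therapy is urgently needed in order to increase the proportion of patients able to undergo alloSCT", and transplant is a secondary endpoint. A patient who responds at the first assessment, has a donor and starts conditioning before finishing course 2 will have no post-course-2 Lugano assessment. That patient is a success on the transplant endpoint and, if in CR, a success on CR after one course. In the primary ORR the same patient could be called a failure, a responder by carrying the first assessment forward, or not assessable.

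If the choice were made after the data were seen, it could move the headline figure. Section 2.1 names failure to respond as one reason patients cannot be transplanted, so those affected are likely to be responders. The number matters because section 14.0 supports n = 21 partly by noting that the lower interval limit at 13/21 equals the 43% ORR seen with ibrutinib plus nivolumab.

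**Working it through.** **1. The plan's own interval.** Inputs from section 14.0: n = 21, 13 responses, beta(0.8, 1.2) prior, 90% interval. The posterior is Beta(0.8 + x, 1.2 + 21 − x). For x = 13 this is Beta(13.8, 9.2), with equal-tailed 90% limits 0.430 and 0.760 and width 0.329. The plan states 0.33 and a lower limit of 43%, so the figure reproduces.

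**2. Effect of the coding.** Let k be the number of the 13 first-read responders who have no post-course-2 assessment because of transplant. The documents give no value for k, so 0 to 2 is an assumption.

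| k | First read carried forward | Coded non-responder | Excluded |
|---|---|---|---|
| 0 | 13/21 = 61.9% (0.430–0.760) | same | same |
| 1 | 13/21 = 61.9% (0.430–0.760) | 12/21 = 57.1% (0.387–0.721) | 12/20 = 60.0% (0.408–0.747) |
| 2 | 13/21 = 61.9% (0.430–0.760) | 11/21 = 52.4% (0.344–0.681) | 11/19 = 57.9% (0.384–0.733) |

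Per patient, non-responder coding costs 1/21 = 4.8 points.

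**3. How long the exposure lasts.** Course 1 runs on days 15–42 and the first assessment falls on day 57. With the two-week gap in section 4.3, course 2 occupies days 57–84, a window of 28 days. Footnote 3 to Table 4 has cycle 2 starting 4 to 8 weeks after cycle 1. Taking day 42 as completion, course 2 then ends on day 98 to day 126, a window of 42 to 70 days. These two passages disagree and must be reconciled, but that is a separate matter. On either schedule the patient must respond, have a donor, be fit and start conditioning within 4 to 10 weeks. Section 2.1 says most patients are not eligible for transplant.

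**4. Does any decision turn on it?** The response stopping limits (0, 0–1, 0–2, 0–3 and 0–4 responses at 6, 9, 12, 15 and 18 patients) recompute exactly from P(rate < 0.4) > 0.9. They are fixed counts and do not change with the coding. As a stress test, assume that 10% or 20% of responders were coded as failures at the interim looks. A true rate of 0.60 then acts as 0.60 × 0.9 = 0.54 or 0.60 × 0.8 = 0.48. At a true toxicity rate of 0.2, the early-stopping probability goes from 0.037 (0.04 in the plan's table) to 0.053 or 0.087. If the looks use the first assessment, there is no effect. Section 14.0 gives no success threshold for the final ORR; the 43% match supports the sample size and is not a test.

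**5. Which coding follows from the text.** The rule in section 10.2 comes directly after the definition of overall response as CR or PR, which is the primary endpoint's own term. No CLL overall response rate appears among the objectives in section 1.0. The same paragraph goes on to discuss telling RT from CLL. An analyst who finds no post-course-2 Lugano assessment and looks for a rule finds this one. The planning fraction 13/21 puts all 21 patients in the denominator.

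**The case for a change.** The best case for a change is that the text does not close the question. The rule sits under a CLL heading, RT is to be assessed separately, and the rule names no time point. A patient with a first assessment is not plainly one with a missing assessment, so carry-forward could be argued later. Section 14.0 also uses the word evaluable without defining it, which leaves exclusion open. One patient coded as a failure or excluded takes the lower limit below 43%, and the remedy would be a few sentences.

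Much of this stands as a point of clarity. The placement is imperfect, and a sentence in section 10.1 naming the post-course-2 time point would do no harm. It is also true that non-responder coding can understate activity if good responders leave early.

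It does not show that the plan goes wrong. The endpoint is response after two courses, so carrying an earlier assessment forward would change the endpoint, while non-responder coding keeps it. The term evaluable governs when a summary goes to the medical monitor; it does not set the ORR denominator. The understatement would be visible, because the transplant proportion and the CR rate after one course are already secondary endpoints and the first assessment is scheduled for everyone. Success on the transplant endpoint alongside non-response on the primary is not a contradiction, since the two measure different things. Early transplant is also only one way to miss the second assessment, and the same default serves the others.

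The summary is timed at 8 weeks, while two 8-week cycles put the second assessment near week 16 (day 56 + 57 = 113). Which assessment the interim looks count is a fair question, but it does not depend on transplant and should be taken up on its own.

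**Conclusion.** No change is needed. This is a gap that an analyst fills sensibly with a conventional rule already in the protocol: no post-course-2 Lugano assessment counts as non-response, over all 21 patients. That reading is conservative and keeps the endpoint as defined.

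The size is 4.8 percentage points of ORR for each affected responder. It is zero if nobody starts conditioning in the window and 9.5 points (2/21) for two patients. No success criterion rests on the figure, and the stopping limits and the plan's interval reproduce as printed.

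The conclusion assumes that the section 10.2 rule is applied to RT, which its wording supports but its heading does not settle, and that the number transplanted early is small, which the documents do not state. The final report can give the number of patients who left for transplant before the second assessment, with their last Lugano result, from data already collected.

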5.0 STUDY MEDICATIONS

5.1 Blinatumomab

5.1.1. Blinatumomab formulation, reconstitution and administration

Blinatumomab will be supplied as 4 mL single-use glass injection vials containing a sterile, preservative-free, white to off-white, lyophilized powder for intravenous (IV) administration following reconstitution with sterile water for injection (sWFI). Each vial contains a target of 38.5 µg

blinatumomab (nominal) formulated with 3.68 mg citric acid monohydrate, 105.0 mg trehalose dihydrate, 25.55 mg lysine hydrochloride, and 0.70 mg polysorbate 80, pH of 7. Following reconstitution with 3 mL sterile water for injection the final concentration of blinatumomab will be 12.5 µg/mL.

Since blinatumomab will be administered via continuous intravenous route, it needs to be stabilized at low concentrations to prevent absorption to surfaces. Therefore, the IV bag must be conditioned by prior addition of a product-specific diluent (IV solution stabilizer - IVSS), resulting in a final diluent concentration of 0.5 mM citrate, 25 mM lysine hydrochloride and 0.002% (w/v) polysorbate 80. IVSS is supplied in 10 mL single-use glass injection vials as a sterile, preservative-free, clear, colorless-to-slightly-yellow liquid concentrate. It consists of 25 mM citric acid monohydrate, 1.25 M L-lysine hydrochloride, and 0.1% (w/v) polysorbate 80, pH of 7. Following dilution in 0.9% NaCl, the ingredient concentrations are 25 mM L-lysine hydrochloride, 0.002% (w/v) polysorbate 80, and 0.5 mM citric acid monohydrate. Sterile water for injection and supplies required for reconstitution and injection of blinatumomab will not be provided to clinical sites.

The drug administration should not be interrupted, if possible. In case of infusion interruption, due to any technical or logistic reason, the interruption should be as short as possible and the infusion continued at the earliest time possible. Every interruption longer than 1 hour should be documented. If the interruption is longer than 4 hours, re-start of the infusion should be performed in the hospital. The subject should be observed overnight for possible side effects after the re-start. Administration of dexamethasone premedication as described in Table 1 is required. If possible, the infusion duration before and after an interruption should total 28 days per treatment cycle (i.e. if interruptions occur, the missed days should be “made up” after re-commencement so a total of 28 days is given). This will not be considered a protocol violation if interruptions occurred for documented medical reasons.

5.1.2 Adverse events associated with blinatumomab

5.1.2.1 General Infusion Reactions

Infusion reactions may be clinically indistinguishable from manifestations of cytokine release syndrome (CRS). Patients should be observed closely for infusion reactions, especially during the

first infusion of the first and second cycles. Management of infusion reactions may require either temporary interruption or discontinuation of blinatumomab.

5.1.2.2 Hepatic/Biliary/Pancreatic

Treatment with blinatumomab was associated with transient elevations in liver enzymes. The majority of these events were observed within the first week of blinatumomab initiation and did not require blinatumomab interruption or discontinuation.

Pancreatitis, life threatening or fatal, has been reported in patients receiving blinatumomab in clinical trials and the post-marketing setting. High-dose steroid therapy may have contributed, in some cases, to the pancreatitis.

5.1.2.3 Immune Cytokine Release Syndrome Cytokine Release Syndrome (CRS)

This may be severe, life-threatening or fatal and was reported in patients receiving blinatumomab. Serious adverse events that may be associated with CRS included pyrexia, asthenia, headache, hypotension, total bilirubin increased, elevation of liver enzymes (AST and ALT). The median time to onset was 2 days. Disseminated intravascular coagulation (DIC) and Capillary leak syndrome (CLS) have been commonly associated with CRS. Hemophagocytic lymphohistiocytosis/macrophage activation syndrome (HLH/MAS) has been uncommonly reported in the setting of CRS.

5.1.2.4 Tumor Lysis Syndrome

Tumor lysis syndrome (TLS), which may be severe, life-threatening or fatal, has been observed in patients receiving blinatumomab. Appropriate prophylactic measures include aggressive hydration and antihyperuricemic therapies (such as allopurinol or rasburicase).

5.1.2.5 Infections

Pneumonia, bacteremia, opportunistic infections, and catheter site infections have been observed, some of which were life-threatening or fatal.

